Isothiocyanate sulforaphane (SF), derived from broccoli sprouts, has been known to induce an antioxidant response through the Keap1-Nrf2-antioxidant response element pathway.¹ With its chemoprotective effects as the rationale, it has previously been studied for tolerance and safety in humans and has been shown to have virtually no adverse effects.²⁻⁴ This includes a study in which sulforaphane-containing broccoli sprout extracts was formulated in acetone and topically applied to the skin. ² Additionally, a recent study has shown that oral sulforaphane was safely tolerated in doses of 50-150 µmol daily in children with autism. ⁵

SF selectively induces K17 and K16 in skin keratinocytes. Local activation of two distinct signaling pathways, hedgehog and Keap1/Nrf2/ARE, rescued skin blistering in an epidermolysis

bullosa simplex mouse model, correlating SF with the reprogramming of keratin synthesis in epidermis and improving skin fragility.⁶

Sulforaphane might also help in maintaining the collagen levels during photoaging via the inhibition of the AP-1 activation and of the MMP expression. A previous study reported that SF had preventive effects on UV-induced MMP expression, inhibiting the MMP-1 and MMP-3 expression by blocking the NF-jB pathway.⁷

Aging of human skin may result from both the passage of time (intrinsic aging) and via exposure to external factors (extrinsic aging) such as sunlight (photoaging).⁸ One hallmark feature of skin aging, regardless of type, is skin thinning or fragility. This is partially due to the breakdown in dermal collagen. An increase in MMP-1 after UV exposure is observed in skin. MMP-1 is an interstitial collagenase able to hydrolyze type I collagen, the major component of the dermis, and plays a crucial role in the disorganization and progressive degeneration of dermal extracellular matrix.⁸

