Date: 06/16/2017 Principal Investigator: [name], MD Application Number: IRB00105668

Group A

Visit 1(day 0):

During the first scheduled appointment, the research protocol will be discussed with the subject and documentation will be obtained of the subject's consent to participate in the study and the subject's agreement to be contacted about future research studies. Photographs and clinical assessment will be taken.

Once informed consent is obtained, investigators will identify two suitable areas on the photoexposed forearm and one suitable area of the photoprotected upper inner arm for study. Each participant will receive up to 14ml of broccoli sprout extract (BSE) in jojoba oil, containing 7000nmol of sulforaphane. 500nmol of sulforaphane will be applied each night on each suitable

area for up to 7 consecutive nights. Additionally, each participant will receive up to 14 ml of jojoba oil only to be applied each night on one of the photoexposed site. All areas will be occluded with saran wrap every night. A demonstration and verbal instructions for how and where to apply study drug will be provided to subjects.

During this visit, investigators will perform clinical assessments, elasticity measurements, and up to two 6 mm punch, one from each area.

Visit 2 (up to day 7):

During this visit, investigators will perform clinical assessment, elasticity measurements and up to three 6 mm punch, one from each area.

Visit 3 (day 10-14): During this visit investigators will remove sutures from biopsies taken on visit 1.

Visit 4 (day 17-21):

During this visit investigators will remove sutures from biopsies taken on visit 2.

Group B

Visit 1:

During the first scheduled appointment, the research protocol will be discussed with the subject and documentation will be obtained of the subject's consent to participate in the study and the subject's agreement to be contacted about future research studies. Photographs and clinical assessment will be taken.

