Once informed consent is obtained, investigators will identify 2 suitable test areas on the photoprotected upper inner arm for study. Test area dimensions will be about 17 x 17 mm in diameter, the spot size produced by the department's UV device. Each participant will receive up to 7 ml of broccoli sprout extract (BSE) in jojoba oil, containing 3500nmol of sulforaphane and up to 7 ml of jojoba oil only 500 nmol of sulforaphane will be applied each night to Test Area #1 for up to 7 consecutive nights. Additionally, jojoba oil only will be applied each night to Test Area #2 for up to 7 consecutive nights. Areas will be occluded with saran wrap every night. A demonstration and verbal instructions for how and where to apply study drug will be provided to subjects. Clinical assessment and elasticity measurements will be performed during this visit as well.

Visit 2:

UV Light Irradiation: Within 1 to 7 days of BSE and jojoba oil only application, investigators will deliver a fixed dose of UV light to Test Area #1 and Test Area #2. Subjects will be asked to return on-site up to 3 days after UV exposure for biopsy.

Visit 3:

During this visit, investigators will perform clinical assessment, elasticity measurements and three 6 mm punch, one from each Test Area and one from normal, unirradiated skin, also on the upper inner arm, to serve as a control.

Visit 4:

Subjects will return on-site 10-14 days after biopsy to have sutures removed.

Photography: Standardized digital photographs will be obtained by study staff using a digital camera and software under standard photographic conditions at each study visit. Participants' eyes will be blacked out to de-identify facial photos. Photograph files will be coded to remove personal identifiers and stored on a secure hard drive in CTReP.

Clinical assessment: Clinical assessments will be performed to 1) record baseline skin findings 2) to identify up to 4 suitable areas for biopsy, 3) give information/demonstration about sulforaphane application and 4) to identify occurrence of any adverse events.

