Skin biopsies: up to five skin punch biopsies (up to 6 mm in diameter) from Group A will be taken in order to conduct the laboratory work. Two from the untreated control areas, two after up to 7 days applying sulforaphane, and one after up to 7 days applying jojoba oil only to a photoexposed site. Up to three skin punch biopsies (up to 6 mm in diameter) from Group B will be taken in order to conduct to the laboratory work. One from control area, one from UV irradiated area after topical jojoba oil only and one from UV irradiated area after topical sulforaphane. All areas will be biopsied using standard punch biopsy tools and following standard clinical protocols, including cleansing the skin with an alcohol wipe and injecting local anesthesia with lidocaine and epinephrine. No more than five total skin biopsies will be obtained from a volunteer over the course of the study. After removal of the tissue sample, one or two sutures are placed to close the circular opening. Sutures are removed and a scar is formed, but typically heals well without complications and blends well with the surrounding skin. Routine post-biopsy care instructions will be provided and volunteers will be instructed to return in 10 to 14 days to have sutures removed and for assessment of healing.

Laboratory studies: Tissue work-up may include but not limited to cryosectioning and immunofluorescence staining and protein or RNA extraction for molecular assays (RT-PCR and/or qPCR for select mRNAs and western blotting for select protein antigens). The levels of keratin 1, keratin 5, keratin 10, keratin 14, keratin 16, keratin 17, and Nrf2 will be studied with both immunofluorescence and RNA PCR. [name] laboratory from the Department of Biochemistry and Molecular Biology and Bloomberg School of Public Health at Johns Hopkins University has successfully applied this strategy.

b. Study duration and number of study visits required of research participants.

The study consists of up to 4 on-site study visits within a 3 week period, including the suture removal visit. We will allow 4 years to complete the study.

c. Blinding, including justification for blinding or not blinding the trial, if applicable. NOT APPLICABLE

d. Justification of why participants will not receive routine care or will have current therapy stopped.

NOT APPLICABLE

e. Justification for inclusion of a placebo or non-treatment group. NOT APPLICABLE

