Jojoba oil was chosen based on its known lipophilic nature and ability to permeate deeply into skin ⁹. In a prior study performed in SKH-1 hairless mice (which feature thicker epidermis, more akin to human than furry mouse strains), topical sulforaphane induced K16 and K17 best when administered in jojoba oil. Dermabase, another widely used vehicle, was also tested in this study; however, as Dermabase was found to induce K16/K17 alone even without sulforaphane

added, it was deemed not to be an appropriate vehicle to measure the effects of sulforaphanecontaining broccoli sprout extract.¹⁰

The equivalent of 500nmol of sulforaphane (delivered in the form of broccoli sprout extract) was chosen as the dosage to be used as it has been previously been shown to be tolerable to human skin up to a dose of 681nmol when it caused a transient 3mm erythematous macule.¹⁰ By using jojoba oil coupled with occlusion under saran wrap, we hope to demonstrate penetration of broccoli sprout extract's effect to the basal layer of the epidermis. Broccoli sprout extract is a natural substance that has been orally ingested for thousands of years. It has been used topically and orally with no adverse events.⁹⁻¹¹

Lidocaine with epinephrine will be used as a local anesthetic to the biopsy sites prior to the biopsy procedure. The drug used in the study will be the same drug provided for the entire Johns Hopkins Department of Dermatology. There will not be a separate batch of this drug for the sole purposes of this study as this study is not a clinical trial and use of the drug is unlikely to interfere with study results.

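### Group B's UV-versus-control contrast also carries jojoba oil and occlusion, so UV without sulforaphane cannot be separated within that group

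*Combined protocol and SAP*

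**What the plan says.** The secondary objective (Section 2) asks how keratin expression changes after acute UV exposure, both on its own and combined with topical sulforaphane. Group B, 20 volunteers, serves that objective.

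- **Sites and treatment (Section 4a, Group B, Visit 1).** "investigators will identify 2 suitable test areas on the photoprotected upper inner arm for study". Test Area #1 gets sulforaphane in jojoba oil each night. For the other, "jojoba oil only will be applied each night to Test Area #2 for up to 7 consecutive nights". The sentence on nightly saran wrap follows directly and refers to these areas.
- **Irradiation (Visit 2).** Both test areas receive UV.
- **Biopsies (Visit 3).** Three are taken: "one from each Test Area and one from normal, unirradiated skin, also on the upper inner arm, to serve as a control". The Skin biopsies paragraph lists the same set: "One from control area, one from UV irradiated area after topical jojoba oil only and one from UV irradiated area after topical sulforaphane".
- **Elasticity.** The Cutometer and Ballistometer paragraphs list the same three conditions after UV: normal skin and the two test areas.
- **Group A.** The areas are "two suitable areas on the photoexposed forearm and one suitable area of the photoprotected upper inner arm for study". The oil-only biopsy is "one after up to 7 days applying jojoba oil only to a photoexposed site".
- **Analysis (Section 7).** Assays and markers are named. No contrast, test or vehicle correction is given.

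One statement does not fit this schedule. The group summary in the recruitment paragraph of Section 4a promises Group B biopsies both ahead of irradiation and a day after it. The visit schedule and the Skin biopsies paragraph include no biopsy of a pretreated area before UV.

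**The concern.** Test Area #2 is the only irradiated site without sulforaphane, so it is the natural source for the UV effect on its own. It differs from the control in three ways: UV, up to seven nights of jojoba oil, and up to seven nights under wrap. No Group B site has oil and wrap without UV, and none has UV without oil and wrap.

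The protocol itself shows that a vehicle can move this endpoint. Section 6 explains that another vehicle was rejected because, in a hairless-mouse study, "Dermabase was found to induce K16/K17 alone even without sulforaphane". If jojoba oil or occlusion shifts keratin expression or skin mechanics, a comparison of Test Area #2 with control that is labelled as a UV effect would include that shift. Section 3 says it is not known whether UV affects epidermal keratins, so this comparison matters to what Group B can conclude.

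**Working it through.** The plan gives no alpha, power, effect size or SD, so it has no figure to reproduce. The check is whether the effects can be separated, followed by an illustration of size.

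**Is the control bare?** The text never says so outright. Three things point that way: it is called normal skin, only two areas are identified at Visit 1, and the oil and wrap instructions name only those two. Supply gives weak support. Group B's extract is 3500 nmol in 7 ml at 500 nmol per application, so 3500/500 = 7 applications of 7/7 = 1 ml. At that volume, 7 ml of plain oil covers one site for seven nights. But Group A receives up to 14 ml of plain oil for one site, so supply does not track sites consistently and proves nothing.

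**Site means.** Let b be untreated upper-inner-arm skin, V the effect of oil plus wrap, U the effect of UV in oiled, wrapped skin, and S the effect of sulforaphane in irradiated skin.

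| Site | Mean |
|---|---|
| Control | b |
| Test Area #2 | b + V + U |
| Test Area #1 | b + V + U + S |

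- Test Area #2 − control = V + U.
- Test Area #1 − Test Area #2 = S.

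There are three means and four unknowns; the design matrix has rank 3. S and the sum V + U are estimable. U alone and V alone are not.

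**Elasticity.** Group B also has readings at Visit 1, before any oil. These add further estimates of b. No reading is scheduled between the start of oil and UV, so the rank stays at 3 and U is still not estimable.

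**With an oiled, wrapped, unirradiated control.** The control mean becomes b + V, and Test Area #2 − control = (b + V + U) − (b + V) = U.

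**Illustration of size.** Assumptions not in the documents: a paired t-test, two-sided 5%, and U = 0. With n = 20 there are 19 degrees of freedom and the critical value is 2.093. If V is d SDs of the paired difference, the test statistic is noncentral t with noncentrality d × √20.

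| d | d × √20 | Chance of a false UV finding |
|---|---|---|
| 0 | 0 | 5.0% |
| 0.2 | 0.894 | 13.6% |
| 0.3 | 1.342 | 24.7% |
| 0.5 | 2.236 | 56.5% |

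**The case against.** **The group summary may supply the comparator.** A biopsy of an already oiled and wrapped area just before UV would be the missing b + V. This is a genuine condition on the point. The visit schedule and the Skin biopsies paragraph are more detailed, agree with each other and contain no such biopsy, so they are the likelier reading. The conflict still has to be resolved.

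**No analysis is written.** A reader might infer that the plan will report Test Area #2 minus control as UV alone. The documents do not support that: Section 7 states no contrast. The objective's wording can also mean UV without sulforaphane, which describes Test Area #2. This objection stands, so mislabelling is a risk and not a stated plan. It does not remove the gap, because even on that wording Test Area #2 has no matched unirradiated comparator.

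**Group A could correct it.** A reader might infer that the UV effect cannot be recovered from the study at all. That goes too far. Group A's oil-only site could estimate V, but it is on photoexposed forearm in other people. It helps only if the vehicle effect is the same at both sites and the two groups are comparable. Group A's sulforaphane-in-oil site on the upper inner arm could be used instead if sulforaphane does not change the UV response, which is part of what Group B asks. The plan adopts neither assumption.

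**Vehicle was considered.** Section 6 shows that jojoba oil was chosen over a vehicle that induced K16/K17, so its own effect may be small. That is fair. But the section gives no figure for jojoba oil alone and does not address any effect of occlusion on keratins.

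**Conclusion.** The point holds for one half of one secondary objective. If the visit schedule governs and the control is bare, Test Area #2 minus control estimates UV plus jojoba oil plus occlusion, for biopsies and for elasticity, and Group B alone cannot separate them.

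The bias equals the oil-plus-wrap effect. The documents give neither its size nor its direction, and it may be nil. The rates of about 14%, 25% and 56% depend on assumed effects and an assumed test; they show sensitivity and do not predict an error rate.

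A reader might also infer that the sulforaphane results are compromised. They are not. Test Areas #1 and #2 share oil, wrap and UV, so their difference is matched. The primary objective belongs to Group A and is unaffected. Section 8 calls the study exploratory, which limits the consequences but does not make the UV contrast interpretable. It should be fixed.

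**What to change.** **Preferred change.** At Visit 1, mark the upper-inner-arm control site. Apply jojoba oil only and wrap on the same nights as the test areas, and leave the site unirradiated. Take the already planned Visit 3 control biopsy and an elasticity reading there. A bare-skin elasticity reading can be kept as well. State that Test Area #2 minus control is then the UV effect in oiled, wrapped skin; it equals the effect on bare skin only if oil and wrap do not alter the UV response.

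**Cost.** No added biopsy or visit. If 1 ml per night is assumed, it needs up to 7 ml more jojoba oil per participant (7 × 20 = 140 ml for the group), plus one more wrapped area. The main loss is the within-person bare-skin biopsy. Whether sulforaphane-pretreated irradiated skin resembles normal skin could then be judged only against other people.

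**If the bare control is kept.** Report the biopsy and elasticity contrasts as UV plus vehicle and occlusion, not as a UV effect. If Group A is used to correct them, say so in advance with the assumptions. Relabelling costs nothing.

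**In either case.** State whether the control site receives oil and wrap, and reconcile the biopsy timing in the Section 4a group summary with the Group B visit schedule and the Skin biopsies paragraph.

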Effect of Topical Sulforaphane on Skin Fragility Seen in Skin Aging and With Ultraviolet Exposure

NCT03126539

June 16, 2017

Date: 06/16/2017 Principal Investigator: [name], MD Application Number: IRB00105668

Johns Hopkins Medicine - eForm A

Effect of Topical Sulforaphane on Skin Fragility Seen in Skin Aging and With Ultraviolet Exposure

1. Abstract

The cross sectional study investigating whether topical application of sulforaphane (broccoli sprout extract) results in the induction of both keratin 16 and keratin 17 in the basal layer of the epidermis is currently IRB approved (IRB00061421).

The primary purpose of our study is to compare the expression of keratins before and after application of sulforaphane (SF) and determine whether these findings alter skin fragility seen in both intrinsic and extrinsic skin aging as well as in ultraviolet (UV) light exposure.

This investigation will be done in collaboration with researchers from the Department of Biochemistry and Molecular Biology and Bloomberg School of Public Health at Johns Hopkins University. The study population recruited by Johns Hopkins Department of Dermatology will include up to 50 individuals over the age of 18 with healthy skin. Each study participant will have four on-site study visits and will be asked to contribute photographs, undergo non invasive elasticity measurements, use topical sulforaphane for 7 days and contribute up to four biopsy specimens for laboratory study. We will also evaluate any differences in keratins' expression in skin exposed to acute UV light, separately and after pretreatment with sulforaphane.

2. Objectives

- The primary objective of this study is to compare the induction of both keratin 16 and keratin 17 in the basal layer of the epidermis in both photoprotected and photodamaged skin treated with sulforaphane to determine whether SF can improve skin fragility seen in these conditions. This would be visualized by established indirect immunofluorescence assays on skin tissue sections prepared from biopsy material, and would be confirmed and quantified by PCR-based analyses of RNA samples.
- The secondary objective is to investigate distinct keratin expression changes in human skin after acute UV light exposure, separately and in combination with application of topical sulforaphane.

3. Background

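### Blinding is marked not applicable with no reason; coded, masked reading of biopsies should be described, and random site assignment added for the two sulforaphane-versus-jojoba contrasts

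*Combined protocol and SAP*

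**What the plan says.** Section 4c answers the blinding item with "Blinding, including justification for blinding or not blinding the trial, if applicable. NOT APPLICABLE". No explanation follows.

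On the outcome, Section 2 says of keratin induction: "This would be visualized by established indirect immunofluorescence assays on skin tissue sections prepared from biopsy material". It adds that the result "would be confirmed and quantified by PCR-based analyses of RNA samples". Laboratory studies in Section 4a lists six keratins "and Nrf2 will be studied with both immunofluorescence and RNA PCR". Section 7 (Study Statistics) names the assays again and gives no reading procedure.

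The coding that is described protects identity. Under Photography, "Photograph files will be coded to remove personal identifiers", and Section 8 mentions de-identification under confidentiality. Neither conceals treatment, site or visit from the person reading a biopsy.

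On sites, the Group A investigators choose "two suitable areas on the photoexposed forearm and one suitable area of the photoprotected upper inner arm", with "jojoba oil only to be applied each night on one of the photoexposed site". In Group B they choose two areas on the upper inner arm; sulforaphane goes to Test Area #1 and jojoba oil to Test Area #2. How an area comes to be numbered 1 is not stated, and randomisation is not mentioned anywhere.

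**The concern.** The Abstract frames the primary purpose as a change in keratin from before to after sulforaphane, and Sections 3 and 6 set out a clear expectation that K16 and K17 will rise. Immunofluorescence involves choosing fields and judging signal. A reader who knows that a section is treated, or is the later one, can shift both. The shift points the same way in each participant, so within-person pairing does not remove it.

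The sulforaphane-versus-jojoba contrasts carry extra weight because all treated areas are occluded, and because Section 6 reports that another vehicle induced K16/K17 by itself in mice. These contrasts are what can separate sulforaphane from oil plus occlusion. They need unprejudiced reading, and they also need the two compared areas to be exchangeable. If one kind of area tended to receive sulforaphane, a pre-existing keratin difference would look like a treatment effect.

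**Working it through.** **1. Which comparisons are exposed.** Let r be the average reader shift towards the treated or later section. Let δ be a pre-existing keratin difference between the two matched areas. Let p be the share of participants in whom the higher-expressing area gets sulforaphane.

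| Comparison | Added to the mean difference |
|---|---|
| Before/after, same area | r |
| Sulforaphane versus jojoba oil (Group A forearm, Group B inner arm) | r + (2p − 1)δ |
| Induction in photodamaged minus photoprotected skin | r(photodamaged) − r(photoprotected), which is zero if the two are equal |

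The third row matters because Section 2 can be read as comparing induction between skin types, whereas the Abstract states a before/after comparison.

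**2. Can a site difference be adjusted out with a baseline biopsy?**
- Group A: three areas are chosen, but Visit 1 allows up to two punches. At least one area therefore has no untreated biopsy of its own. Two untreated biopsies are planned, so the group is not without a baseline.
- Group B: the visit schedule takes all three punches at Visit 3, and Skin biopsies lists one control and two post-UV specimens. The Recruitment paragraph of Section 4a, however, speaks of biopsies both before and 24 hours after irradiation. On the first two texts, neither test area has its own baseline.

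A systematic site difference could therefore not be fully adjusted out.

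**3. Illustrative size.** There is no figure in the plan to reproduce. Assumptions: no true effect, a two-sided paired t-test at 0.05, and shifts in units of the SD of the paired difference. Section 4a gives 20 volunteers per group; 15 and 10 pairs show the effect of losses.

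*Fully consistent shift* (a reader shift, or a site difference with p = 1). The t statistic is noncentral with parameter d√n. For d = 0.3 and n = 20 this is 0.3 × 4.472 = 1.342. The critical value on 19 degrees of freedom is 2.093, and the rejection rate is 0.247.

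| Shift d (SD) | 20 pairs | 15 pairs | 10 pairs |
|---|---|---|---|
| 0.1 | 0.071 | 0.065 | 0.059 |
| 0.2 | 0.136 | 0.112 | 0.088 |
| 0.3 | 0.247 | 0.192 | 0.136 |
| 0.5 | 0.565 | 0.438 | 0.293 |

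*Site difference with partly lopsided placement*, 20 pairs, no reader shift. The paired difference is N(0,1) plus δ with probability p, or minus δ otherwise (400,000 simulated trials per cell).

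| δ (SD) | p = 0.9 | p = 0.7 | p = 0.5 (randomised) | Mean shift at p = 0.7: (2 × 0.7 − 1)δ |
|---|---|---|---|---|
| 0.1 | 0.063 | 0.053 | 0.050 | 0.04 |
| 0.2 | 0.105 | 0.063 | 0.050 | 0.08 |
| 0.3 | 0.172 | 0.078 | 0.050 | 0.12 |
| 0.5 | 0.371 | 0.123 | 0.050 | 0.20 |

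**4. Which safeguard comes first.** With a reader shift and a site difference of 0.3 SD each, randomising the site alone still leaves a rejection rate of 0.231, because the reader part is untouched. Masked reading therefore ranks ahead of site randomisation.

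**The case against.** The strongest reply is that PCR is the readout the plan calls quantified, that it leaves little room for expectation, and that no immunofluorescence score is specified to which the rates above would apply. This stands in part. PCR is real protection already in the plan, so it would be wrong to say that masked reading is the only safeguard or that all biopsy results are equally exposed. But the objective concerns the basal layer, and no section says that the RNA comes from that layer alone. PCR therefore cannot fully stand in for the section reading.

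Second, the two compared areas lie in the same body region, and the numbers 1 and 2 are only labels. A reader might infer that sulforaphane always goes to the same anatomical position. The documents do not say so; they only leave the choice unstated. With partial imbalance and modest site differences the effect is small, which is why site randomisation is secondary here.

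Third, Section 8 calls the study exploratory, and Section 6 says it is not a clinical trial (there explaining why no separate anaesthetic batch is kept). This limits how much weight the point should carry, but it does not make masked reading inapplicable.

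Fourth, the laboratory may mask in practice. That is possible: silence in the plan does not show that slides are read unmasked. If masking is done, it is easily stated.

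**Conclusion.** The point holds as a gap in the described safeguards, and it should be closed. The plan rules blinding out without a reason although masked biopsy reading is both applicable and inexpensive. The main exposure is the immunofluorescence reading of the before/after change and of the two vehicle contrasts. The absence of a site-assignment rule is a lesser weakness confined to the vehicle contrasts.

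A reader might infer that the results will be invalid, or that 25% or 56% is this study's error rate. The documents support neither. They give no SD, test or alpha, so every bias size above is an assumption and the rates show only how sensitive a 20-pair comparison would be. Confidence is high on what the text omits, not on the size of any bias.

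**What to change.** 1. **Main: masked biopsy reading.** Label tubes, slides and section images with codes that hide treatment, site and visit. Process each participant's samples in one staining and PCR batch, in random order, where storage allows. Have existing staff who do not read slides hold the key, and break the code only after data lock.
2. **Secondary: site assignment, for the two vehicle contrasts only.** Once the matched areas are identified, use a pre-made random list to decide which gets sulforaphane and which gets jojoba oil (forearm in Group A, upper inner arm in Group B).
3. **Text.** Replace the entry in Section 4c with this procedure, and state any unblinding that remains, such as photoexposure or UV change visible in the section. Reconcile the Recruitment paragraph with the Group B visit schedule and the Skin biopsies paragraph on whether a biopsy is taken before irradiation.

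**Cost.** Labels, a key and a list; no extra visits, biopsies or participants. Batching means that Group A Visit 1 samples wait for Visit 2 (up to day 7), which assumes they can be stored. It is also assumed that existing staff can hold the key, since staffing is not described. A lost key or a mislabelled area would lose that participant's pair.
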